### Resumption of Study Drug

If a convincing alternative etiology is identified for the elevated transaminases (ALT, AST, gamma glutamyl transpeptidase, alkaline phosphatase, and total bilirubin), study drug may be resumed when transaminases return to baseline or are  $\leq 2 \times$  ULN, whichever is higher. Approval of the medical monitor is required before resumption of study drug. Upon resumption of study drug, transaminases must be assessed weekly for 4 weeks. If a protocol-defined transaminase elevation occurs within 4 weeks of rechallenge with the study drugs, then the study drugs must be discontinued, regardless of the presumed etiology.

#### **11.6.2.2 Hyperkalemia**

Subjects with a potassium level that is  $\leq 0.4$  units below the ULN at the Day 1 or Day 57 Visit will be required to have a blood sample collected for a repeat evaluation of plasma potassium within 7 ( $\pm 2$ ) days.

The standard of care for management of hyperkalemia should be applied. A thorough investigation of potential causes should be conducted, and the subject's potassium level should be followed closely.

If hyperkalemia occurs, inhaled study drug should be interrupted until the plasma potassium has stabilized in the normal range. If no convincing temporary or possibly reversible alternative etiology (e.g., oral intake of potassium, acute renal failure, metabolic acidosis, uncontrolled diabetes mellitus, admission of repeated fist-clenching during phlebotomy, hemolyzed sample) for the elevated potassium is identified, study drug treatment must be discontinued regardless of whether the level has improved; this decision should be made in consultation with the medical monitor. Subjects in whom treatment is discontinued for elevated potassium should have their potassium levels monitored closely until levels normalize or return to baseline.

#### **11.6.3 Physical Examinations and Vital Signs**

A full physical examination of all body systems and vital signs assessment will be performed at the Screening Visit, ETT Visit, and Safety Follow-up Visit (see [Table 3-1](#) and [Table 3-4](#)). At other visits, abbreviated physical examinations will be performed before dosing with inhaled study drug (see [Table 3-3](#)).

A physical examination includes a review of the following systems: head/neck/thyroid; eyes/ears/nose/throat (EENT); respiratory; cardiovascular; lymph nodes; abdomen; skin; musculoskeletal; and neurological. Breast, anorectal, and genital examinations will be performed when medically indicated. After screening, any clinically significant abnormal findings in physical examinations will be reported as AEs.

The abbreviated physical examination will include an assessment of the following body systems: head/neck/thyroid, EENT, cardiovascular system, respiratory system, skin, and abdomen.

Vital signs include blood pressure (systolic and diastolic), temperature, pulse rate, and respiration rate. These will be assessed following a 5-minute rest in the seated or supine position.

#### **11.6.4 Electrocardiograms**

Standard 12-lead ECGs will be performed using a machine with printout according to the Schedule of Assessments ([Table 3-1](#), [Table 3-3](#), and [Table 3-4](#)). Additional standard 12-lead ECGs will be performed at any other time if clinically indicated. During the Treatment Period,

the ECG will be performed 60 ( $\pm$  30) minutes after the completion of inhaled study drug dosing. The performance of all ECGs will adhere to the following:

- The subject will be instructed to rest in the seated or supine position for at least 5 minutes before having an ECG performed.

The ECG traces will be read manually at the study site at the Screening Visit and Safety Follow-up Visit. A printout of the ECG traces will be made for safety review by the investigator and maintained with source documentation. Clinically significant ECG abnormalities occurring during the study through the Safety Follow-up Visit will be recorded as AEs.

To ensure safety of the subjects, a qualified individual at the study site will make comparisons to baseline measurements. If the QTcF is increased by  $>45$  msec from the baseline or an absolute QTcF value is  $\geq 500$  msec for any scheduled ECG, 2 additional ECGs will be performed approximately 2 to 4 minutes apart to confirm the original measurement. If either of the QTcF values from these repeated ECGs remains above the threshold value ( $>45$  msec from baseline or  $\geq 500$  msec), a single ECG will be repeated at least hourly until QTcF values from 2 successive ECGs fall below the threshold value that triggered the repeat measurement.

If the QTcF value remains above the threshold value ( $>45$  msec from the average of the 3 predose values on Day 1 or  $\geq 500$  msec) on repeated measurement or is noted on  $>2$  occasions with no identified alternative etiology for the increased QTcF, then discontinuation from study drug treatment may be required after discussion with the medical monitor.

Subjects in whom treatment is discontinued for increased QTc should have their QTc monitored closely until it normalizes or returns to baseline.

### **11.6.5 Ophthalmologic Examination**

All pediatric subjects  $<18$  years of age will undergo an ophthalmologic examination at the Screening Visit. Pediatric subjects  $<18$  years of age at the Screening Visit who complete the Day 84 Visit will have an ophthalmologic examination that is to occur between the Day 84 Visit and the Safety Follow-up Telephone Contact. Pediatric subjects who discontinue from study drug treatment will have an ophthalmologic examination that is to occur between their last dose of study drug and completion of either the ETT Visit or the Safety Follow-up Visit.

The ophthalmologic examination includes

- measurement of best corrected distance visual acuity of each eye;
- measurement of lens refracting power (e.g., autorefractor or ophthalmoscopy streak following cycloplegia); and
- pharmacologically-dilated examination of the lens with a slit lamp.

These examinations must be conducted by a licensed ophthalmologist or optometrist. The screening ophthalmologic examination must be completed and the results reviewed before enrollment. The Screening Visit ophthalmologic examination does not need to be repeated if there is documentation of an examination that met protocol criteria, and that it was conducted within 3 months before the Screening Period, or if there is documentation of bilateral lens removal.

In addition, at the Screening Visit, the following history will be obtained for all subjects:

- History of steroid use
- History or presence of diabetes
- Any prior ophthalmologic or optometric examinations
- History of trauma to the eye
- Any family history of glaucoma, congenital cataracts, or cataracts arising later in life
- Use of corrective lenses (contact lenses or eyeglasses)
- History of prolonged exposure to sunlight or ultraviolet light and use of sunglasses
- History of exposure to secondhand smoke

If a clinically significant lens opacity or cataract is identified at Screening, the medical monitor must be notified. Additional ophthalmologic examinations may be required if a lens opacity or cataract is identified at Screening. The medical monitor should be notified of any additional ophthalmologic examinations.

### **11.6.6 Spirometry**

Refer to Section [11.5.1](#) for the spirometry assessment.

### **11.6.7 Contraception and Pregnancy**

The effects of VX-371 on conception, pregnancy, and lactation in humans are not known.

The effects of lumacaftor/ivacaftor on conception, pregnancy, and lactation in humans are not known. Neither lumacaftor nor ivacaftor showed any genotoxic potential in a standard battery of *in vitro* (Ames, Chinese hamster ovary cell chromosomal aberration) and *in vivo* (mouse micronucleus) studies. Lumacaftor and ivacaftor were each found to be non-teratogenic in reproductive toxicology studies in rats and rabbits (see the lumacaftor/ivacaftor Investigator's Brochure). However, a metabolite of lumacaftor, M28-lumacaftor, given to pregnant rats at very high levels far beyond levels observed in humans (>100-fold) produced fetal malformations. The significance of this finding in humans is unclear, but is highly unlikely to be of any clinical significance. Subjects should follow the contraception requirements outlined in this study protocol. The effects of lumacaftor/ivacaftor on the PK of hormonal contraceptives are not known; however, since lumacaftor is an inducer of CYP3A, it may reduce the effectiveness of hormonal contraceptives.

#### **11.6.7.1 Contraception**

Participation in this study requires a commitment from the subject and his/her partner to use at least 1 acceptable method of contraception, which must be used correctly with every act of sexual intercourse. Methods of contraception should be in successful use from at least 14 days before the first dose of study drug (unless otherwise noted) and until 90 days following the last dose of study drug.

#### **Contraception for the couple is waived for the following:**

- True abstinence for the subject, when this is in line with the preferred and usual lifestyle of the subject. Periodic abstinence (e.g., calendar, ovulation, symptothermal, postovulation methods) and withdrawal are not acceptable methods of contraception.

- If the male is infertile (e.g., bilateral orchiectomy). Infertility may be documented through examination of a semen specimen or by demonstration of the absence of the vas deferens by ultrasound before the first dose of the study drug.
- If the female is of non-childbearing potential, per the following:
  - Documented hysterectomy or a bilateral oophorectomy/salpingo-oophorectomy.
  - Postmenopausal: continuous amenorrhea for at least 12 months and serum FSH levels  $\geq 40$  mIU/mL.
  - Has not achieved menarche (has not had her first menstrual period). If a female achieves menarche during the study, she will need to follow acceptable methods of contraception or abstinence.

**For subjects for whom contraception methods are not waived due to one of the reasons cited above, the following are acceptable contraceptive methods:**

**Table 11-4    Acceptable Methods of Contraception**

Male subjects and their female (non-study) partners	
 
• Male vasectomy 6 months or more previously, with a negative post-vasectomy semen analysis for sperm
 
• Male or female condom with or without spermicide (either as a single product if commercially available and/or allowed according to local regulations; otherwise condom and spermicide as separate products)
 
• Female bilateral tubal ligation performed at least 6 months previously
 
• Female diaphragm, cervical cap, or vaginal sponge, each with spermicide (where available).
 
• Female continuous use of an intrauterine device (non-hormone releasing or hormone releasing) for at least 90 days
 
• Female combined (estrogen and progestogen-containing) or progestogen-only hormonal contraception associated with inhibition of ovulation if successfully used for at least 60 days
 

Female subjects and their male (non-study) partnersa	
 
• Male vasectomy 6 months or more previously, with a negative post-vasectomy semen analysis for sperm
 
• Male or female condom with or without spermicide (either as a single product if commercially available and/or allowed according to local regulations; otherwise condom and spermicide as separate products)
 
• Female bilateral tubal ligation performed at least 6 months previously
 
• Female diaphragm, cervical cap, or vaginal sponge, each with spermicide (where available).
 
• Female continuous use of an intrauterine device (non-hormone releasing) for at least 90 days
 

a Hormonal contraceptives are not considered an acceptable method in female study subjects because of the potential for a drug-drug interaction with lumacaftor/ivacaftor resulting in reduced exposure and contraception failure; however, female subjects are not required to discontinue their use of hormonal contraceptives as long as they agree to use an acceptable method of contraception as described above.

**Important notes:**

- Hormonal contraceptives are not considered an acceptable method in female study subjects because of the potential for a drug-drug interaction with lumacaftor/ivacaftor resulting in reduced exposure and contraception failure; however, female subjects are not required to

discontinue their use of hormonal contraceptives as long as they agree to use an acceptable method of contraception as described in [Table 11-4](#).

- Local requirements may prohibit the use of some of these acceptable methods listed above. Please contact the medical monitor with any questions.
- If applicable, additional contraception requirements may need to be followed according to local regulations and/or requirements.
- Male and female subjects who are not sexually active at the time of screening must agree to follow the contraceptive requirements of this study if they become sexually active.
- Female condom used with male condom (as a double method of contraception) is not an acceptable method of contraception due to risk of tearing; a different acceptable method of birth control must be used as described in [Table 11-4](#).
- Male subjects must not donate sperm after the first dose of study drug, throughout the study, and for 90 days following the last dose of study drug.
- Female subjects and female partners of male subjects should not plan to become pregnant during the study through 90 days following the last dose of study drug.
- Female subjects should not nurse a child from the start of study drug dosing through 90 days following the last dose of study drug.

Unique situations that may not fall within the above specifications may be discussed with the medical monitor on an individual basis.

#### **11.6.7.2      Pregnancy**

Subjects will be counseled to inform the investigator of any pregnancy that occurs during study treatment and for 90 days after the last dose of study drug(s).

If a subject or the female partner of a male subject becomes pregnant while participating in the study, study drug must be permanently discontinued immediately. The investigator must notify the medical monitor and Vertex GPS within 24 hours of the site's knowledge of the subject's (or partner's) pregnancy using the Pregnancy Information Collection Form.

The subject or partner will be followed until the end of the pregnancy and the infant will be followed for 1 year after the birth, provided informed consent is obtained. A separate ICF (and assent form, if applicable) will be provided to explain these follow-up activities. Pregnancy itself does not constitute an AE.

## **12            STATISTICAL AND ANALYTICAL PLANS**

This section presents a summary of the planned analyses for this protocol. Statistical analysis details will be provided in the Statistical Analysis Plan (SAP), and clinical pharmacologic analysis details will be provided in the Clinical Pharmacology Analysis Plan (CPAP), both of which will be finalized before the clinical database lock for the study and treatment unblinding.

#### **12.1           Sample Size and Power**

The primary efficacy endpoint is the absolute change in ppFEV1 from study baseline to the Day 28 measurements in each Treatment Period.

The null hypothesis to be tested is that the mean change from study baseline in ppFEV1 to the Day 28 measurements is the same for VX-371 in combination with HS versus HS alone.

To have a feasible sample size and study duration, this study uses a crossover design. Assuming a standard deviation (SD) of 7 percentage points, 50 subjects per sequence are needed to have an approximately 81% power to detect a 3 percentage point treatment difference in the mean absolute change in ppFEV1 from study baseline at Day 28 between VX-371 + HS and HS alone. The study will have an approximately 80% power to detect a 3 percentage point (within treatment) change from baseline at Day 28 in ppFEV1 for VX-371. A 2-sided significance level of 0.05 was used in the sample size calculations. The sample size also takes into consideration an assumed dropout rate of 10%.

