To have a feasible sample size and study duration, this study uses a crossover design. Assuming a standard deviation (SD) of 7 percentage points, 50 subjects per sequence are needed to have an approximately 81% power to detect a 3 percentage point treatment difference in the mean absolute change in ppFEV1 from study baseline at Day 28 between VX-371 + HS and HS alone. The study will have approximately 80% power to detect a 3 percentage point (within treatment) change from baseline at Day 28 in ppFEV1 for VX-371. A 2-sided significance level of 0.05 was used in the sample size calculations. The sample size also takes into consideration an assumed dropout rate of 10%.

The primary efficacy endpoint is the absolute change in ppFEV1 from study baseline at Day 28 in each Treatment Period. The primary efficacy analysis is based on a mixed-effects model. This model will include the absolute change from study baseline in ppFEV1 at Day 28 as the dependent variable, study baseline for ppFEV1, treatment, and period as fixed effects, and subject nested within sequence as a random effect. The within-subject covariance will be assumed to have the compound symmetry structure. Denominator degrees of freedom for the F-test for fixed effects will be estimated using the Kenward-Roger approximation. No imputation of missing

data will be done. Assuming that the subjects have dropped out at random, an estimate of treatment effect will be based on such subjects and will then be combined with the estimate from subjects who have data in both treatment periods with weights based on the precision of these estimates.

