## **8.2           Rationale for Study Design and Study Drug Regimens**

### **8.2.1       Study Design**

This Phase 2a, randomized, double-blind, placebo-controlled, incomplete block, crossover, multicenter study in subjects  $\geq 12$  years of age with CF who are homozygous for the *F508del-CFTR* mutation and receiving stable Orkambi treatment is designed to evaluate the safety, efficacy, and PK of treatment with VX-371 in 4.2% HS compared to 4.2% HS alone.

A randomized, double-blind, placebo-controlled study design was selected to avoid observer bias and reduce symptoms or outcomes arising from the investigator's or the subject's knowledge of treatment. A crossover design in which subjects are randomized to 1 of 4 treatment sequences will enable within-subject comparison of selected treatment effects with increased statistical power. A 28-day washout period is judged to be of sufficient duration for all subjects to return to their baseline values for FEV1 and to accommodate synchronization with cycling inhaled antibiotics.

There are 2 primary endpoints; the first is to evaluate safety and tolerability, and the second is to evaluate efficacy as measured by the absolute change in ppFEV1 from study baseline at Day 28 in each Treatment Period. Although the primary objectives are to evaluate the safety and efficacy of VX-371 in 4.2% HS versus 4.2% HS alone, 2 additional treatment sequences will compare VX-371 in 0.17% saline (placebo) versus 0.17% saline (placebo). These comparisons will provide insight with respect to the effect of VX-371 alone and inform design options for future studies. Even though 2 different concentrations of saline will be used, the double-blind will be maintained with respect to VX-371 because allocation to this component will remain unknown to both investigators and subjects.

A sample size of approximately 150 subjects is considered feasible and is expected to provide sufficient data to evaluate the efficacy, safety, and PK of VX-371 formulated with and without HS. The unbalanced randomization ratio permits more subjects to be used to address the primary study objective.

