### 12.3.1 General Considerations

All individual subject data for those randomized or exposed to inhaled study drug will be presented in data listings.

**Continuous variables** will be summarized using the following descriptive summary statistics: number of subjects (n), mean, SD, standard error (SE), median, minimum value (min), and maximum value (max). The precision of the measurement for each continuous variable will be specified in the SAP.

**Categorical variables** will be summarized using counts and percentages. Percentages will be presented to 1 decimal place.

**Treatment emergent (TE) period** for Treatment Period 1 will correspond to data from the first dose of inhaled study drug in the first period to the safety evaluation visit (28 days after the last dose in the first period and prior to the first dose of Treatment Period 2). Similarly, the TE period for Treatment Period 2 will correspond to data from the first dose of inhaled study drug in Treatment Period 2 through the Safety Follow-up Telephone Contact, or 28 days after the last dose in the second period for subjects who do not have a Safety Follow-up Telephone Contact.

**Baseline:** For this crossover study, 2 types of baseline will be defined. The **study baseline** is defined as the most recent nonmissing measurement (scheduled or unscheduled) collected before the first dose of inhaled study drug in the study. Study baseline will be used for all summaries of demographics, background, and baseline characteristics as well as all efficacy data analyses, including the primary endpoint analysis. In addition, **period baseline** is defined as the most recent nonmissing measurement (scheduled or unscheduled) collected before the first dose of inhaled study drug in each treatment period. For Treatment Period 2, the baseline value should be from an assessment measured after the TE period for Treatment Period 1. Period baseline will be used for all safety data analyses. For ECG, baseline for Period 1 will be defined as the average of the 3 pretreatment measurements on Day 1.

**Absolute change from study baseline** will be calculated as post-baseline value – study baseline value.

**Absolute change from period baseline** will be calculated as post-baseline value – period baseline value.

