## 7.2 Sample Size and Power

The primary efficacy endpoint is the absolute change in ppFEV1 from study baseline to the Day 28 measurements in each Treatment Period.

The null hypothesis to be tested is that the mean change from study baseline in ppFEV1 to the Day 28 measurements is the same for VX-371 in combination with HS versus HS alone.

To have a feasible sample size and study duration, this study uses a crossover design. Assuming a standard deviation (SD) of 7 percentage points, 50 subjects per sequence (VX-371 + 4.2% HS followed by 4.2% HS; 4.2% HS followed by VX-371 + 4.2% HS) are needed to have approximately 81% power to detect a 3 percentage point treatment difference in the mean absolute change in ppFEV1 from study baseline at Day 28 between VX-371 + HS and HS alone. The study will have approximately 80% power to detect a 3 percentage point (within treatment) change from study baseline at Day 28 in ppFEV1 for VX-371. A 2-sided significance level of 0.05 was used in the sample size calculations. The sample size took into account an assumed dropout rate of 10%.

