##### **9.3.1.2 Primary Analysis of Primary Efficacy Endpoint**

The null hypothesis to be tested is that the mean change from study baseline in ppFEV1 at Day 28 is the same for VX-371 with HS versus HS alone.

[figure not shown]
The primary analysis of the primary efficacy endpoint will be based on a mixed-effects model. This model will include the absolute change from study baseline in ppFEV1 at Day 28 as the dependent variable and the following fixed effects: treatment, period and ppFEV1 at study baseline and subject as a random effect. The within-subject covariance will be assumed to have the compound symmetry (CS) structure. Denominator degrees of freedom for the F-test for fixed effects will be estimated using the Kenward-Roger approximation.

[figure not shown]
No imputation of missing data will be performed. Subjects who have data only for one of the periods will have a data structure similar to a parallel-group trial. Assuming that these subjects have dropped out at random, an estimate of treatment effect based on such subjects will be combined with the estimate from subjects who have data in both treatment periods with weights based on the precision of these estimates.

[figure not shown]

[figure not shown]
where “primary efficacy endpoint” is the absolute change from study baseline in ppFEV1 at day 28.

[figure not shown]
Descriptive summary statistics including n, mean, SD, and least-square means (LS means), along with its SE, 95% CI and the within-treatment 2-sided *P* value will be provided by treatment group. The between-treatment LS mean differences [VX-371 + HS versus HS, VX-371 + HS versus VX-371 + placebo, VX-371 + HS versus placebo, and VX-371 + placebo versus placebo] with the corresponding SE, 95% CIs and 2-sided *P* values will be presented. The cumulative distribution of the absolute change from study baseline in ppFEV1 at Day 28 will be plotted by treatment group.

[figure not shown]

[figure not shown]

[figure not shown]

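### Do the 81% and 80% powers contradict each other because both rest on one undefined SD of 7?

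*Protocol*

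**What the plan says.** Protocol section 12.1 gives one variability figure and two powers. The first is for the primary contrast: "Assuming a standard deviation (SD) of 7 percentage points, 50 subjects per sequence are needed to have an approximately 81% power" to detect a 3-point difference in mean absolute change in ppFEV1 from study baseline at Day 28. The second reads: "The study will have an approximately 80% power to detect a 3 percentage point (within treatment) change from baseline at Day 28". Both use a two-sided 0.05 level and allow for 10% dropout. The synopsis repeats the pair of figures. SAP section 7.2 also repeats them (50 per sequence "are needed to have approximately 81% power to detect a 3 percentage point treatment difference", then "The study will have approximately 80% power to detect a 3 percentage point (within treatment) change from study baseline at Day 28"), and the only relevant difference is that it names study baseline for the second figure.

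None of the three places says whether 7 is the SD of a subject's change, the within-subject SD or the SD of the paired difference. No correlation between periods is stated. The 80% has no number of subjects and no SD of its own, and its arm is given only as VX-371.

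Three other statements bear on the correlation:

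- Study baseline is used for "as well as all efficacy data analyses, including the primary endpoint analysis" (Protocol section 12.3.1), so both of a subject's changes subtract the same value.
- The primary model has ppFEV1 "at study baseline and subject as a random effect" (SAP section 9.3.1.2).
- Protocol section 8.2.1 says the crossover "will enable within-subject comparison of selected treatment effects with increased statistical power".

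**The concern.** The SD of a paired difference and the SD of a single change are linked by the correlation between the two changes. One value of 7 can serve both powers only if that correlation takes a particular value. On the most natural reading that value is about zero, which a crossover trial is not normally designed around: the shared baseline and stable differences between subjects should make the two changes positively correlated.

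If the correlation is positive, one stated power looks wrong. Either the primary power is well above 81%, so that 50 per sequence are more than 81% requires, or the 80% for VX-371 alone is too high. A reader could worry that the trial is larger than necessary, or that the smaller sequences promise more than they can deliver. Protocol section 8.1 lets the sponsor stop sequences 3 and 4 while protecting power in sequences 1 and 2, and section 8.2.1 says the VX-371-alone comparison will inform later studies. The basis of the powers therefore seemed worth settling.

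**Working it through.** **Inputs.** Difference 3, SD 7, two-sided 0.05 and 10% dropout are from Protocol section 12.1. The sequence sizes of 50, 50, 25 and 25 are from Table 8-1. Completers are 0.9 × 100 = 90 in sequences 1 and 2, and 0.9 × 50 = 45 in sequences 3 and 4. Taking VX-371 without HS as the arm for the 80%, with n = 45, is an inference: Table 10-1 labels that product VX-371, and section 12.1 writes VX-371 + HS when it means the combination. Powers are from the noncentral t distribution.

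**Reproducing 81%.** With 7 as the SD of change and correlation ρ, the paired-difference SD is 7 × √(2(1 − ρ)). At ρ = 0 this is 7 × √2 = 9.90.

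- SE = 9.90/√90 = 1.043; noncentrality = 3/1.043 = 2.875; df 88; power **81.2%**.
- Ninety is the smallest number of completers that reaches 81%, and 90/0.9 = 100, exactly 50 per sequence.
- Taking 7 as the SD of the paired difference gives 98.0%, so that was not the reading used.

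**Reproducing 80%.** One-sample test with SD of change 7 and n = 45.

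- SE = 7/√45 = 1.043; noncentrality = 2.875; df 44; power **80.3%**.

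The two standard errors are equal because 7√2/√90 = 7/√45. The powers differ only through the degrees of freedom, which accounts for the stated gap of one point.

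**What a positive correlation would do.** The documents give no value; 0.1 to 0.5 is assumed here for illustration.

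| ρ | 7 = SD of change: primary power, 90 completers | Completers for 81% | 7 = within-subject SD: power for VX-371 alone, n = 45 | Change detectable with 80% power |
|---|---|---|---|---|
| 0 | 81.2% | 90 | 80.3% | 2.99 |
| 0.1 | 85.0% | 81 | 76.0% | 3.15 |
| 0.2 | 88.9% | 73 | 71.1% | 3.34 |
| 0.5 | 98.0% | 46 | 51.1% | 4.23 |

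If 7 is the SD of change, the one-sample power does not involve ρ and stays at 80.3%. If 7 is the within-subject SD, the SD of change is 7/√(1 − ρ); primary power then stays at 81.2% for every ρ, and only the second figure falls.

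**A second reading that also fits.** Within-subject SD 7, ρ = 0.5 and the within-treatment test on VX-371 + HS with 90 completers: SD of change = 7/√0.5 = 9.90 and power = 81.2%, close to the stated 80%. It requires VX-371 to mean the combination, which the wording does not favour.

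**The case for a change.** The strongest case for a change is that two incompatible sets of assumptions fit the same sentence and that the SAP, where the details were to appear, repeats it unresolved. At zero correlation the crossover contrast has about the power of a parallel trial with 90 per arm (81.6%), which sits oddly beside the rationale in section 8.2.1. A correlation of only about 0.05 moves one of the two figures by 2 points. If 7 is the within-subject SD, power for VX-371 alone could be 71% to 51% at correlations of 0.2 to 0.5. Three short clarifications would settle it.

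The description of the gap stands: the SD, the correlation, and the arm and number behind the 80% are not written down. The consequences do not follow.

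- The SD appears in the same sentence as the mean absolute change from study baseline, so the plain reading is the SD of that change. On that reading a positive correlation can only raise primary power.
- The branch in which 80% is overstated needs a within-subject SD that none of the three statements mentions, together with an inferred arm and an inferred number. It is also sensitive to that number: with n = 50 and a correlation of 0.1 the within-treatment power is 80.5%.
- No decision rests on the 80%. The provision in section 8.1 protects only the two primary sequences, lets the other two stop, and says all planned analyses go ahead whatever the numbers enrolled. The comparison in section 8.2.1 is VX-371 in 0.17% saline against 0.17% saline, whereas the 80% concerns a change from baseline within one treatment.

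**Conclusion.** The concern does not hold as an arithmetic error. Both stated powers reproduce from one SD of 7 at the planned numbers: 81.2% against about 81%, and 80.3% against about 80%. This rests on three things the documents leave unstated: 7 is the SD of change from study baseline, the planning correlation is zero, and the 80% refers to VX-371 without HS with 45 completers. The exact match of 90 completers to 100 randomized supports the first two.

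On that reading 81% is a floor. At assumed correlations of 0.2 to 0.5 the primary power would be 89% to 98%, and 81% would need about 41 down to 26 randomized per sequence (73/0.9 and 46/0.9, rounded up to 82 and 52 in total). Planning without credit for an unknown correlation is a fair trade-off in a Phase 2a trial, which also has to collect safety data.

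What remains is a reporting gap. The primary model estimates its variance components from the trial data, so the planning SD and correlation do not enter the estimates, confidence intervals or P values. Writing the assumptions down would help a reader, but it would alter no sample size, analysis or conclusion.
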